Assessment of risks versus benefits requires some description of the individuals to be treated. The study population is at high risk for a number of cognitive and psychiatric problems; this is also a population at high risk for treatment failure, either by treatment dropout or continued illicit substance use. The behavioral therapies tested here carry minimal risk and will be implemented as adjuncts to standard outpatient treatment at this comprehensive treatment center. We believe we have included adequate safeguards for participants to address the ethical questions, regular contacts with program staff and close monitoring of symptoms, and procedures to withdraw from study treatments participants who show significant deterioration or adverse events. Thus, the potential benefits for individuals and society at large are high; and the risk/benefit ratio appears favorable toward the proposed study treatments.

We will recruit participants via flyers distributed at the clinic and via direct referral from clinicians, following procedures we have worked out through multiple previous studies at this site (86-94). The

screening of patients using the inclusion and exclusion criteria, and the urine toxicology screens and SCIDs, will minimize the risk of including participants who are not appropriate for this low-risk study. On-site medical staff and frequent visits and monitoring by research staff will minimize the risks of adverse events and assure that they are managed quickly if they do occur. Study physicians are available on call, including nights and weekends, to answer patient concerns.

Participants will be withdrawn from the treatment arm if they show severe psychological or symptomatic deterioration, unacceptable levels of adverse events as determined by the SATU/IOP program director or if clinically necessary for ethical or safety purposes. Participants dropped from the study for these reasons or because they wish to withdraw will be offered treatment as usual at SATU/IOP or be referred to a higher level of care, such as an inpatient facility, when appropriate. For all participants, if an emergent medical, psychiatric, or substance abuse issue emerges from any treatment or test given as part of the proposed study, these will be assessed through the SATU/IOP physician and appropriate referral or treatment will be delivered. Private referral and/or hospitalization may also be offered according to the participants' needs and wishes.

12. **Data and Safety Monitoring Plan:** Include an appropriate Data and Safety Monitoring Plan (DSMP) based on the investigator's risk assessment stated below. (Note: the HIC will make the final determination of the risk to subjects.)
 - a. What is the investigator's assessment of the overall risk level for subjects participating in this study? **Minimal risk**
 - b. If children are involved, what is the investigator's assessment of the overall risk level for the children participating in this study? **N/A**
 - c. Include an appropriate Data and Safety Monitoring Plan. Examples of DSMPs are available here <http://your.yale.edu/policies-procedures/forms/420-fr-01-data-and-safety-monitoring-plans-templates>

1. Procedures to ensure the validity and integrity of the data

Multiple measures are in place to ensure the validity and integrity of the data. First, all research staff receive Human Subjects Protection training, as well as training in Good Clinical Practice. Weekly research meetings for all research staff take place, in addition to weekly project-specific measures, as a forum for in-service training as well as to discuss questions regarding issues that arise in complex clinical research protocols. Adherence to protocol procedures will be monitored using individual supervision conducted by the PI. Multiple research staff are cross-trained to 'cover' for each other; thus, review by multiple staff with oversight by the PI facilitates early identification of errors and oversight. The Data Manager conducts weekly quality assurance checks of research charts and Case Report Form (CRFs).

2. Procedures to guarantee the accuracy and completeness of the data during data collection, entry, transmission, and analysis.

As CRFs are completed, they are scanned in and processed by the Data Manager. The electronic images are verified by the Data Manager using Teleforms, and transferred to the database. The Data Manager processes the assessments on a daily basis, checks for missing data, logical inconsistencies, and reports any errors back to the Research Assistants. Any necessary corrections are done by direct entry and documented in the system and on the CRF logs.

3. Data and Safety Monitoring Board

A Data and Safety Monitoring Board (DSMB) will monitor the proposed project because this population might be considered vulnerable due to their substance use. This board, already in place for all projects affiliated with the P50 Psychotherapy Development Center (PDC), is composed of Yale investigators who are independent of the parent trials and experienced in various aspects of the conduct of clinical trials for the treatment of addictive disorders (Drs. [name], [name], and [name]). [name] has developed a standard DSMB report form that has been used in all PDC and PDC-related trials that summarizes on a quarterly basis:

1. Recruitment, retention, and follow-up rates for the study and compares them to target rates.
2. Rates of data completeness and availability of primary outcome data
3. Occurrence of AEs and SAEs
4. Report of study progress since the last report.
5. Rates of recruitment of women, minorities, and children with respect to targeted rates.

These reports will be generated by the Data Managers each quarter, signed and reviewed by [name] prior to their submission to the DSMB.

Because the projected effect sizes may not be large enough for detection during interim analyses, we are not proposing a preliminary analysis of accumulating efficacy and safety data by treatment assignment. Instead, we propose to submit a quarterly report of aggregate data to the DSMB members that contains screening data, baseline demographics, retention data, serious adverse events data, as well as accrual status including projections, times to milestones, and any other data that will help in the assessment of the clinical trial. Based on this report, each DSMB member will complete a form making one of two recommendations: 1) continue recruitment as planned; or 2) schedule formal DSMB meeting immediately. If any DSMB member recommends a meeting, this will be scheduled within one week, minutes will be kept, the report will be reviewed with the PI, and the committee will vote on whether the study should: 1) continue recruitment unchanged; 2) continue with a protocol amendment; 3) stop recruiting pending further investigation. If, after this meeting, any DSMB member votes to stop recruitment or requests a protocol modification, the Yale IRB will be informed.

4. Reporting of Serious Adverse Events (SAEs)

SAEs will be systematically assessed at each clinic visit. We have worked out these procedures in multiple clinical trials of behavioral interventions). The most common SAEs are expected to be overnight hospitalizations for reasons related to substance use, psychiatric, or medical problems. All events meeting FDA definition for SAEs (any medical occurrence that results in death; is life-threatening; requires inpatient hospitalization or prolongation of existing hospitalization; creates persistent or significant disability/incapacity, or a congenital anomaly/birth defect will be reported) will result in immediate notification (within 1 hour of staff learning of SAE) to the study Principal Investigator ([name]), Psychotherapy Development Center (PDC) regulatory coordinator, and on-site SATU/IOP clinic director (or their designee). Within 24 hours, staff will complete the study SAE Form (without PHI) and send this to the same three individuals.

As part of this initial report, [name] will provide an evaluation of the SAE with regard to its: 1) grade of risk (none, mild, moderate, severe, life-threatening or disabling; fatal; 2) attribution of relatedness to study (unrelated/not, unlikely/remote, possibly, probably, definitely); 3) level of anticipation/expectedness given the risks of study population or protocol (anticipated, anticipated but at frequency greater than expected, unanticipated); 4) categorization (death, life threatening, hospitalization, disability, birth anomaly/defect, medical intervention required to prevent death/disability); 5) resolution (recovered/resolved, recovering/resolving, not recovered/resolved, fatal, lost to follow-up). This evaluation will be documented on study SAE Form. The PDC regulatory coordinator or designee will follow up with [name] or study staff until the SAE resolution (5) is considered resolved and any updates documented and reported appropriately.

The Yale Human Investigations Committee (HIC) must be informed with 5 days of any SAE that [name] judges to be unanticipated (or anticipated but occurring greater than expected) and (possibly, probably, definitely) related to study participation. The HIC form must be completed either electronically through COEUS, faxed to the HIC office, or hand delivered. A copy of this HIC form will be forwarded to the PDC regulatory coordinator or designee. Yale's File Transfer Facility or other secure system must be used if personal health information is included on this form.

The NIDA Program Office must be informed of any SAE that results in death or which [name] judges as sufficiently life threatening that death might have occurred if medical or psychiatric intervention were not provided. This report is made to NIDA regardless of whether the SAE was study related or unanticipated. [name] and study staff will provide a follow-up report to the PDC regulatory coordinator or designee with 48 hours of the event so that NIDA's SAE form can be completed and submitted. Copies of this form will be distributed to the PDC PI ([name]), study co-investigators, all DSMB members, and the on-site program director. Yale's File Transfer Facility or other secure system must be used if personal health information is included on this form. Within one week, the PDC PI or Scientific Director will confer with DSMB members to determine if a meeting should occur.

In addition to the SAE forms completed, a progress note in the study clinical chart must be made that provides a detailed narrative description of the event with a co-signature by supervisory personnel.

All SAEs regardless of grade, relatedness, anticipation, categorization, or resolution will be summarized in quarterly DSMB reports and annual reports to the Yale HIC.

We will report all major protocol amendments or changes in the informed consent form to the NIDA Project Officer as well as any temporary or permanent suspension of patient accrual

- d. For multi-site studies for which the Yale PI serves as the lead investigator: **N/A**
 - i. How will adverse events and unanticipated problems involving risks to subjects or others be reported, reviewed and managed? *Write here*
 - ii. What provisions are in place for management of interim results? *Write here*
 - iii. What will the multi-site process be for protocol modifications? *Write here*

13. **Statistical Considerations:** Describe the statistical analyses that support the study design.

Version Date: 03022019

Version 3

Data will be collected, managed and analyzed through the standard procedures of the PDC as described in detail in the parent grant. Regarding statistical power, [name] previous study using a similar cognitive remediation battery (1) with 55 participants revealed an effect size of $d = .42$ for the malleability of performance on the training, with 92% power. A sample size of 100 will allow us to evaluate the effect of ongoing substance use as a moderator of treatment response at 80% power. We have established that we can recruit and treat a sample of this size in the one-year time allotment of the SOBC supplement. Our rates of end of treatment assessment and follow-up in Center trials is 90% or above, enabling us to conduct true intention to treat analyses with minimal statistical imputation (48, 49, 83). General Linear Modeling will be used to examine change in performance on these tasks over time. Using General Linear Modeling as we have in previous Center-supported studies (10, 37, 49, 57, 84), we will evaluate the extent to which participants who receive cognitive remediation show significantly greater improvement across time in the cognitive-affective assessment battery than those who receive the control training. Additionally, structural equation modeling (SEM) and latent profile analysis (LPA) will be used to examine variable-centered (correlation between measures) versus person-centered (profiles of individuals) alternatives. SEM with maximum-likelihood estimation will be used to test the association between pre-post measures and SUD-related behaviors. LPA, whereby each individual is assigned to a mutually exclusive assay class (i.e. profile) based on a data-driven analytic strategy, will be used to test the association between each individual's pre-post profile and treatment response. Moreover, we will use regression discontinuity analyses compare observations clustered closely on either side of a process-level threshold around a particular intervention. This analysis would allow us to examine the local average treatment effects on pre-post measures in a non-parametric data-driven manner.

Timeline	1	2	3	4	5	6	7	8	9	10	11	12
Recruit 3 participants/week	x	x	x	x	x	x	x	x	x			
Participant 100 completes 4 week treatment											x	
Participant 100 completes 1 month follow-up												x
Data analysis and preparation of reports												x

SECTION II: RESEARCH INVOLVING DRUGS, BIOLOGICS, RADIOTRACERS, PLACEBOS AND DEVICES

If this section (or one of its parts, A or B) is not applicable, check off N/A and delete the rest of the section.

A. RADIOTRACERS

N/A

If NO, an FDA issued IND is required for the investigational use unless RDRC assumes oversight.

B. DRUGS/BIOLOGICS

N/A

Note: If the YNHH IDS (or comparable service at CMHC or WHVA) will not be utilized, explain in detail how the PI will oversee these aspects of drug accountability, storage, and preparation.

4. Use of Placebo: Not applicable to this research project

B. DEVICES

N/A

SECTION III: RECRUITMENT/CONSENT AND ASSENT PROCEDURES

1. Targeted Enrollment: Give the number of subjects:

- a. Targeted for enrollment at Yale for this protocol: 100
- b. If this is a multi-site study, give the total number of subjects targeted across all sites: N/A

2. Indicate recruitment methods below. Attach copies of any recruitment materials that will be used.

 Flyers	 Internet/web postings (Criagslist)	 Radio
 Posters	 Mass email solicitation	 Telephone
 Letter	 Departmental/Center website	 Television
 Medical record review*	 Departmental/Center research boards	 Newspaper
 Departmental/Center newsletters	 Web-based clinical trial registries	 Clinicaltrails.gov
 YCCI Recruitment database	 Social Media (Twitter/Facebook):	
 Other: Direct referral from clinicians to RA		

* Requests for medical records should be made through JDAT as described at <http://medicine.yale.edu/ycci/oncore/availableservices/datarequests/datarequests.aspx>

3. Recruitment Procedures:

- a. Describe how potential subjects will be identified. Flyers and direct clinician referral. Flyers will be posted throughout SATU, IOP, and on websites (Criagslist, Department/Center website). Additionally, all clinicians will be given a "Client Interest Sheet" that describes the basic study and asks clients to contact study personnel.

Clinicians will mention, in-person, that a study is being conducted at SATU/IOP. If a client expresses interest, the clinician will have the client fill out the "Client Interest Sheet."

- b. Describe how potential subjects are contacted. Potential participants will be contacted via two options. One option will be that the client takes a flyer tab and calls the research staff via phone. That phone call will be used to set up an in person screen, where a consent form will be presented. The other option will be that a clinician provides the client with a "Client Contact Sheet" and then the client calls staff to set-up an initial in-person screen.
- c. Who is recruiting potential subjects? Research staff and indirectly clinic staff who refer

4. Assessment of Current Health Provider Relationship for HIPAA Consideration:

Does the Investigator or any member of the research team have a direct existing clinical relationship with any potential subject?

- Yes, all subjects
- Yes, some of the subjects
- No

If yes, describe the nature of this relationship. *Write here*

5. Request for waiver of HIPAA authorization: (When requesting a waiver of HIPAA Authorization for either the entire study, or for recruitment purposes only. Note: if you are collecting PHI as part of a phone or email screen, you must request a HIPAA waiver for recruitment purposes.) **N/A**

Choose one:

- For entire study
- For recruitment/screening purposes only
- For inclusion of non-English speaking subject if short form is being used and there is no translated HIPAA research authorization form available on the University's HIPAA website at hipaa.yale.edu.

- i. Describe why it would be impracticable to obtain the subject's authorization for use/disclosure of this data: *Write here*
- ii. If requesting a waiver of **signed** authorization, describe why it would be impracticable to obtain the subject's signed authorization for use/disclosure of this data: *Write here*

The investigator assures that the protected health information for which a Waiver of Authorization has been requested will not be reused or disclosed to any person or entity other than those listed in this application, except as required by law, for authorized oversight of this research study, or as specifically approved for use in another study by an IRB.

Researchers are reminded that unauthorized disclosures of PHI to individuals outside of the Yale HIPAA-Covered entity must be accounted for in the "accounting for disclosures log", by subject name, purpose, date, recipients, and a description of information provided. Logs are to be forwarded to the Deputy HIPAA Privacy Officer.

6. Process of Consent/Accent: Describe the setting and conditions under which consent/assent will be obtained, including parental permission or surrogate permission and the steps taken to ensure subjects' independent decision-making.

Version Date: 03022019

Version 3

A trained research staff member will obtain written informed consent prior to any study related procedures. The informed consent process will be conducted in a private, quiet setting. The staff member and the participant will discuss the basic components described in the consent form. These include: participation is voluntary and participants may withdraw without consequences to clinic services received, purpose, procedures, randomization, visit schedule, risks and benefits, potential compensation, alternatives to study participation, and confidentiality. The consent form describing each of these components will be reviewed and approved by the Yale School of Medicine Institutional Review Board (Human Investigations Committee) prior to enrolling any participants. Potential participants will be provided an opportunity to ask questions and time to consider his/her decision to participate. A comprehension quiz will be given to ensure the participant has an adequate understanding of study as we have done in multiple previous studies (87, 93, 95-97). A copy of the consent form will be given to the participant.

7. **Evaluation of Subject(s) Capacity to Provide Informed Consent/Accent:** Indicate how the personnel obtaining consent will assess the potential subject's ability and capacity to consent to the research being proposed.

We require participants to read and write in English, and we routinely use a multiple-choice test after review of the consent form to determine that participants understand the key points of the research. The research staff reviews the test with the participant and clarifies any question which was incorrectly answered.

8. **Non-English Speaking Subjects:** Explain provisions in place to ensure comprehension for research involving non-English speaking subjects. If enrollment of these subjects is anticipated, translated copies of all consent materials must be submitted for approval prior to use.

N/A

As a limited alternative to the above requirement, will you use the short form* for consenting process if you unexpectedly encounter a non-English speaking individual interested in study participation and the translation of the long form is not possible prior to intended enrollment? YES NO

Note* If more than 2 study participants are enrolled using a short form translated into the same language, then the full consent form should be translated into that language for use the next time a subject speaking that language is to be enrolled.

Several translated short form templates are available on the HRPP website (yale.edu/hrpp) and translated HIPAA Research Authorization Forms are available on the HIPAA website (hipaa.yale.edu). If the translation of the short form is not available on our website, then the translated short form needs to be submitted to the IRB office for approval via modification prior to enrolling the subject. *Please review the guidance and presentation on use of the short form available on the HRPP website.*

If using a short form without a translated HIPAA Research Authorization Form, please request a HIPAA waiver in the section above.

9. **Consent Waiver:** In certain circumstances, the HIC may grant a waiver of signed consent, or a full waiver of consent, depending on the study. If you will request either a waiver of consent, or a waiver of signed consent for this study, complete the appropriate section below.

Version Date: 03022019

Version 3

Not Requesting any consent waivers

SECTION IV: PROTECTION OF RESEARCH SUBJECTS

Confidentiality & Security of Data:

1. What protected health information (medical information along with the HIPAA identifiers) about subjects will be collected and used for the research?

No PHI will be collected on study CRFs. We only collect protocol session dates which are changed to "number of sessions completed" if data sets are released to other Yale investigators.

2. How will the research data be collected, recorded and stored?

All research staff and clinicians receive annual Good Clinical Practice, Human Subjects Protection, and HIPAA training through the Yale School of Medicine. Our data collection and management procedures are fully compliant with HIPAA. In addition:

- Our study forms have been designed to avoid collecting identifiable information (e.g., no PHI is collected on CRFs). We generally collect only protocol session dates. These are changed to 'number of sessions completed' if data sets are released to other Yale investigators.
- Research data are collected on CRFs, and sent to data managers in our research offices on a closed secure network. All computers used by research staff are password protected. No identifying information is on CRFs.
- The screening of patients using the inclusion and exclusion criteria, and the comprehensive evaluations will minimize the risk of including subjects with insignificant substance use (or who are otherwise inappropriate for the study).
- Confidentiality in regards to collected materials will be maintained via a numbered reference system maintained by the Project Director. Participants' names will appear only on the consent form, HIPPA authorization form, and "key" form kept by the Project Director.
- Limits to confidentiality include only disclosure of acute suicidality, homicidality, or abuse of a minor, as is standard in clinical practice.
- Data are stored at our secure data management center; data sets do not include identifying information. At the conclusion of the study, all locator data are destroyed. Source data is generally destroyed 3 years after completion of the study at a secure location and destroyed by Shred-It.
- The funding agency, NIDA, may access the data for routine audits.

3. How will the digital data be stored? CD DVD Flash Drive Portable Hard Drive Secured Server Laptop Computer Desktop Computer Other
4. What methods and procedures will be used to safeguard the confidentiality and security of the identifiable study data and the storage media indicated above during and after the subject's participation in the study?

See above

All portable devices must contain encryption software, per University Policy 5100. If there is a technical reason a device cannot be encrypted please submit an exception request to the Information Security, Policy and Compliance Office by clicking on url <http://its.yale.edu/egrc> or email [contact]

5. What will be done with the data when the research is completed? Are there plans to destroy the identifiable data? If yes, describe how, by whom and when identifiers will be destroyed. If no, describe how the data and/or identifiers will be secured.

Data are stored at our secure data management center; data sets do not include identifying information. At the conclusion of the study, all locator data are destroyed. Source data is generally destroyed 3 years after completion of the study at a secure location and destroyed by Shred-It.

6. If appropriate, has a Certificate of Confidentiality been obtained?

Will be applied for pending HIC approval. The Certificate of Confidentiality is being obtained to protect client's omission of substance use and/or a toxicology screen. If the participant tests positive, results will be stored as a part of our research record on the secure server.

SECTION V: POTENTIAL BENEFITS

Potential Benefits: Identify any benefits that may be reasonably expected to result from the research, either to the subject(s) or to society at large. (Payment of subjects is not considered a benefit in this context of the risk benefit assessment.)

The major potential benefit to participants is in potential reduction of substance use and improvements in cognitive affective functioning via the study treatments, which may, in turn, foster improvement in participants' legal, medical, interpersonal, psychological and occupational functioning.

SECTION VI: RESEARCH ALTERNATIVES AND ECONOMIC CONSIDERATIONS

1. **Alternatives:** What other alternatives are available to the study subjects outside of the research?

Individuals who do not wish to participate or who are ineligible for the trial will continue to receive standard treatment at SATU/IOP.

2. **Payments for Participation (Economic Considerations):** Describe any payments that will be made to subjects, the amount and schedule of payments, and the conditions for receiving this compensation.

All participants will be offered compensation for time spent completing study assessments including \$35 for the pre-treatment assessment, \$10 for each training session, \$35 for posttreatment assessment, \$50 bonus for completing all training sessions and scheduled assessments and \$50 for the one-month follow-up. The possible total is \$250 for completing all timepoints. Payments to the participants will be prorated for those who withdraw prematurely; that is, they will receive payment only for those assessments they complete.

3. **Costs for Participation (Economic Considerations):** Clearly describe the subject's costs associated with participation in the research, and the interventions or procedures of the study that will be provided at no cost to subjects.

Subjects will not be charged for ancillary treatments or evaluations they receive at the clinic. Subjects will be charged for treatment as usual at the clinic; where most patients receive treatment with no-out of pocket expenses or on a sliding scale.

4. **In Case of Injury:** This section is required for any research involving more than minimal risk, and for minimal risk research that presents the potential for physical harm (e.g., research involving blood draws).

This is a minimal risk trial with no foreseen injury risks. The participant's insurance carrier will be expected to pay the costs of medical care. No additional financial compensation for injury is available.

- a. Will medical treatment be available if research-related injury occurs? No
- b. Where and from whom may treatment be obtained? The emergency room or private provider
- c. Are there any limits to the treatment being provided? Yes
- d. Who will pay for this treatment? Patient insurance
- e. How will the medical treatment be accessed by subjects? By self- referral

IMPORTANT REMINDERS

Will this study have a billable service? **Yes** **No**

A billable service is defined as any service rendered to a study subject that, if he/she was not on a study, would normally generate a bill from either Yale-New Haven Hospital or Yale Medical Group to the patient or the patient's insurer. The service may or may not be performed by the research staff on your study, but may be provided by professionals within either Yale-New Haven Hospital or Yale Medical Group (examples include x-rays, MRIs, CT scans, specimens sent to central labs, or specimens sent to pathology). Notes: 1. There is no distinction made whether the service is paid for by the subject or their insurance (Standard of Care) or by the study's funding mechanism (Research Sponsored). 2. This generally includes new services or orders placed in EPIC for research subjects.

If answered, "yes", this study will need to be set up in OnCore, Yale's clinical research management system, for Epic to appropriately route research related charges. Please contact [contact]

Are there any procedures involved in this protocol that will be performed at YNHH or one of its affiliated entities?

Yes **No**

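### The quarterly DSMB report pools serious adverse events over both arms, on a detectability argument that supports having no interim test but not leaving out a descriptive table by arm

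*Protocol*

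**What the plan says.** All references are to the Protocol, Section I.12, Data and Safety Monitoring Plan. The SAP does not mention safety monitoring.

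- **The exclusion (item 3).** The investigators write that "we are not proposing a preliminary analysis of accumulating efficacy and safety data by treatment assignment". Efficacy and safety are ruled out together.
- **The reason (same sentence).** "Because the projected effect sizes may not be large enough for detection during interim analyses". No other reason is given.
- **The replacement.** "Instead, we propose to submit a quarterly report of aggregate data to the DSMB members that contains screening data, baseline demographics, retention data, serious adverse" (the quote breaks off at the SAE item). The list goes on to accrual status and "any other data that will help in the assessment of the clinical trial". The standard report form lists "Occurrence of AEs and SAEs" without saying that they are split by arm.
- **The decision.** "Based on this report, each DSMB member will complete a form making one of two recommendations": continue recruitment, or hold a formal meeting at once. If a meeting is held, its vote can change or stop recruitment.
- **Other routes to the board (item 4).** For deaths and life-threatening SAEs, the form sent to the funder is copied to "study co-investigators, all DSMB members, and the on-site program director". Beyond that, "All SAEs regardless of grade, relatedness, anticipation, categorization, or resolution will be summarized in quarterly DSMB reports". Neither statement says that the arm is shown.

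**The concern.** The sentence gives one reason and applies it to two different things. Low power is a reason not to run an interim test. A table of SAE counts by arm is not a test, so low power does not argue against it.

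The arm matters here because of the kind of SAE expected. Item 4 expects mostly overnight hospitalizations for substance use, psychiatric or medical problems. Such events happen in this population without any study intervention, so judging relatedness case by case is hard, and the randomized control arm is the natural comparator. Item 4 also lets an SAE be classed as expected in kind but more frequent than expected, yet the documents state no expected frequency. With neither a reference rate nor a comparison between arms, the board has little to set a pooled count against.

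An arm-specific difference is a fair question. The remediation arm trains under distress and includes a task that gives a loud noise after errors, while the control arm plays a word game (Section I.4, Interventions). That is not evidence of harm. At stake is whether the board's planned quarterly evidence could show an imbalance if one arose.

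**Working it through.** The plan states no figure on this point, so there is none to reproduce. The check asks whether the stated reason holds for efficacy, whether it carries over to safety, and what pooling hides.

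**Inputs from the documents.** N = 100 in two arms; recruitment of 3 per week; d = .42, the only effect size given, for training performance in an earlier study (Section I.13 and SAP).

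**Assumptions.** 1:1 allocation (urn randomization is stated, a ratio is not), two-sided alpha of .05, d = .42 used as the standardized difference between arms, one SAE per participant, quarters counted from first enrolment. All SAE rates and counts below are hypothetical.

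**1. Efficacy.** One quarter enrols 3 × 13 = 39 and two quarters 78. With n per arm, power = Φ(d√(n/2) − 1.96) + Φ(−d√(n/2) − 1.96); the second term is negligible.

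| N | d√(n/2) | Power |
|---|---|---|
| 39 | .42 × √9.75 = 1.31 | 26% |
| 78 | .42 × √19.5 = 1.85 | 46% |
| 100 | .42 × √25 = 2.10 | 56% |

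The stated reason is sound for an interim efficacy test.

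**2. A formal safety test.** Exact power of Fisher's test for assumed SAE rates:

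| Rates | N = 78 | N = 100 |
|---|---|---|
| 5% vs 15% | 17% | 24% |
| 5% vs 20% | 40% | 51% |
| 5% vs 25% | 63% | 75% |

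Detectability therefore also argues against a formal interim safety test.

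**3. What the pooled count hides.** With n per arm and 8 events, the probability of a split a/b is C(n,a)·C(n,b)/C(2n,8). For 8/0 in either direction:

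- 50 per arm: 2 × 536,878,650 / 186,087,894,300 = 0.0058.
- 39 per arm: 2 × 61,523,748 / 23,446,881,315 = 0.0052.

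| Split of 8 SAEs | Fisher p, 50 per arm | Fisher p, 39 per arm | Pooled report |
|---|---|---|---|
| 4/4 | 1.00 | 1.00 | 8 |
| 6/2 | 0.27 | 0.26 | 8 |
| 7/1 | 0.059 | 0.056 | 8 |
| 8/0 | 0.006 | 0.005 | 8 |

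The p-values only show how far apart the splits are that one pooled number covers. They are not proposed as a monitoring rule.

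**4. Timing.** At 3 per week, 100 participants take 100/3 = 33 weeks. Reports at weeks 13 and 26 fall within recruitment; one at week 39 comes after it. The columns for 39 per arm describe the second report, when a vote on recruitment still matters.

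**The case against.** The strongest case on the other side has four parts.

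**Safety is covered in other ways.** Every SAE is notified within an hour and assessed for grade, relatedness and expectedness. Related SAEs that are unanticipated or too frequent go to the ethics committee within five days. Board members receive the forms for deaths and life-threatening events and are consulted within a week on whether to meet. Any one member can force a meeting. This stands. A reader might infer that the board is barred from seeing harm by arm, or that its vote serves no purpose. The documents do not support that: they say what the investigators do not propose, not what the board may not request, and the open-ended item in the report could take more data. What remains is that no route is said to show the arm, and that the open-ended item belongs to a report described as aggregate, straight after analysis by arm is excluded.

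**The reason may be meant for safety too.** The text does not confine its reason to efficacy, although the only effect size in the documents is a performance measure. Step 2 above shows that a formal safety test would also have low power. This stands against a test. It does not reach a table without one.

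**The event counts are invented.** They are, and they are labelled so. A reader might take 8 SAEs as a forecast; the documents give no rate.

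**The trial is low risk.** Both arms do computer tasks for four weeks on top of usual care, and the investigators rate the study minimal risk. This stands and limits the weight of the point.

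**Conclusion.** The point holds as a cheap improvement to oversight, not as a defect that endangers the trial. The plan excludes safety data by arm on a ground that justifies only the absence of a formal test. Its quarterly report is aggregate, and no other section gives the board SAE counts by arm. Because background hospitalizations are the expected SAE, the pooled count is weak evidence for the decision the board is asked to make each quarter.

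The size cannot be stated as a risk, since the documents project neither an SAE rate nor a safety effect. The comparison of 4/4 with 8/0 rests on equal arms and one event per participant, and serves as illustration only. The conclusion itself rests on the text and does not depend on those numbers.

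A reader might also infer that the principal investigator screens what the board sees. The report is signed and reviewed before it is submitted, but the reviewer's name is removed from the public text, so that inference cannot be drawn.

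**What to change.** In Section I.12, item 3:

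1. Keep the statement that there will be no interim efficacy analysis.
2. Take safety data out of the exclusion.
3. Add to the quarterly report a closed table of AEs, SAEs and training withdrawals by coded arm (A/B), with the number randomized to each. It is descriptive, with no test and no stopping boundary.
4. State that the Data Managers send this table to the DSMB, and that it is kept out of the part of the report that the study team reviews.

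The cost is one extra table each quarter. Sample size, alpha and the final analysis do not change. The downside is that small counts can be over-read; a line on the table saying that it is descriptive, and that the board may ask for case narratives before drawing any conclusion, would limit this.
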